8.4.1 Pre-medications Prior to Naxitamab Infusions

Pre-medication is needed to mitigate expected AEs with naxitamab. These include pain, infusion-related reactions, hypotension, allergic reactions, nausea/vomiting and potentially anxiety.

Infusion with naxitamab is associated with pain that may be severe. The pain may involve the abdomen, lower back, chest, legs and arms. The duration may vary but, for most patients, the pain lasts for a couple of hours, and tends to be worst during the naxitamab infusion, subsiding approximately 15 min after end of infusion. Due to the pain, patients may “hold their breath”. A marked variation in the naxitamab-associated pain may be observed from infusion to infusion, and hence the recommended opioid dosages below are applicable only to the first infusion. Opioid pre-medications for mitigation of pain during subsequent infusions of naxitamab and pain medications after completion of the naxitamab infusion should be adjusted at the discretion of the investigator.

All medications (including opioid usage) should be captured on the concomitant medication eCRF.

At home

To reduce the risk of pain, gabapentin should be administered from Day -3 to Day 12 of each cycle according to local SoC (e.g., dose of 5 to 10 mg/kg with a max dose of 600 mg).

It is recommended to titrate to the final effective dose during the first 3 days of treatment:

Day -3: Once daily; Day -2: Twice daily; Day -1 and until Day 10: 3 daily doses (please refer to [Appendix 2](#) if the patient has discontinued IT treatment due to toxicity).

After completion of the naxitamab treatment (i.e. Day 10), it is recommended to taper off the gabapentin treatment: Day 11: Twice daily; Day 12: Once daily. If nerve pain lingers, the patient may continue gabapentin on twice daily dosing for up to a week post naxitamab treatment before further weaning.

At hospital

- Saline solution 0.9% (to reduce risk of severe hypotension)
 - Patients should be preloaded with saline 0.9% infusion 10mL/kg over 1 hour just prior to the start of all naxitamab infusions
- Opioids
 - Per os (PO) opioids are preferred over IV to diminish IV related side effect such as hypotension, respiratory depression, and/or decreased responsiveness
 - Oxycodone 0.1 – 0.2 mg/kg with a max dose of 5 mg PO (45 – 60 min before naxitamab infusion) **or** equivalent dose of PO opioids **or**

- In cases where PO administration is not feasible (15 min before naxitamab infusion):

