4 Not to be performed at EOT if the patient discontinues treatment due to PD, provided that PD is documented by scan and/or biopsy (see Section 9.1.2).

5 Should be performed on D-4 prior to GM-CSF administration

6 Bilateral aspirates and biopsies (2+2): After C2, C4 C8 and EOT (**Cycles in the HITS regimen included**) (see Section 9.1.2).

- For patients with CR or PR after 8 cycles: Assessments will furthermore be performed after C11
- For patients with MR or SD after 8 cycles: Assessments will furthermore be performed after C10, C12
- Samples for RTqPCR should be taken after C2 and C4

All response assessments (except EOT) should be performed before D1 of next cycle.

In addition, for patients who achieve:

- a first CR or PR after C4 OR
- a first CR or PR after C8

a confirmatory response assessment should be performed within 4-6 weeks after detection of the overall response.

7 Imaging schedule follows timing of BM biopsies (see #6 above). For a FDG PET scan, the patient must be in fasting state for at least 4 hrs prior to the scan. If the patient is not fasting serum glucose determination must be performed prior to the administration of FDG (PET scan only). Please refer to the imaging charter for more details.

8 For patients who have not experienced PD, response assessment should be performed at approximately every 4 months after EOT during long-term FU (see Section 9.1.2).

Pre-medication:

Gabapentin should be administered from Day -4 to Day 7 of each cycle according to local SoC (e.g. dose of 5 to 10 mg/kg with a max dose of 600 mg). It is recommended to titrate to the final effective dose during the first 3 days of treatment:

- Day -4: once daily
- Day -3: twice daily
- Day -2 and onwards until Day 7: 3 times daily

Treatment

The treatment regimen/cycles are different for patients who are treated with naxitamab + GM-CSF alone compared to patients who are treated with HITS. Please see below:

Each treatment cycle is 28 days.

GM-CSF:

GM-CSF should be administered sc at 250 µg/m² per day from Day -4 to Day 0 and 500 µg/m² per day at Day 1 to Day 5. The patient/parents will be asked to fill in records of administration (patient diary).

If any events occur fulfilling a GM-CSF discontinuation criterion the patient must discontinue GM-CSF but will be allowed to continue naxitamab treatment, see Section 7.12

Naxitamab:

On days when co-administered with GM-CSF, naxitamab infusion is started ≥ 60 min after GM-CSF.

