Naxitamab should be infused IV at 3 mg/kg/day on Days 1, 3, and 5 for a total dose of 9 mg/kg per cycle. Administration of naxitamab should be adjusted according to Section 8.4.5 if selected naxitamab adverse reactions are observed. If any events occur fulfilling a general

discontinuation criterion the patient must be withdrawn from naxitamab and GM-CSF treatment immediately and enter long-term follow-up, see Section [7.12](#).

Naxitamab should be infused over approx. 30 min.

Special circumstances:

The infusion may be given over approximately 60 min. at Day 1 of any cycle at the investigator's discretion if:

- The patient during the C1D2 infusion (HITS regimen) experienced naxitamab related hypotension:
 - CTCAE Grade 4 **or**
 - Grade 3 not adequately responding
- At the investigators discretion due to severe infusion related adverse drug reactions not adequately responding to interventions

The 60/30 min infusion time is a minimum infusion time. If infusion pause or infusion rate reduction is required due to infusion related AE (see Section [8.4.5](#)) the infusion time will become longer.

Table 13 Treatment with naxitamab + GM-CSF alone

Treatment days in cycles of 28 days	-4 to 0	1	2	3	4	5	6+7	11-28
Premedication (analgesics and/or antihistamines) (8.4.1)	X	X	X	X	X	X	X	
GM-CSF 250 μ g/m ² /day s.c (8.4.6) ¹	X							
GM-CSF 500 μ g/m ² /day s.c (8.4.6) ¹		X	X	X	X	X		
Naxitamab 3 mg/kg/day IV (9mg/kg/cycle) ¹ (8.1.2.3) ¹		X		X		X		

¹ Patients achieving a CR or PR should receive 8 naxitamab cycles or 5 additional naxitamab cycles following the OR, whichever provides the longest treatment with naxitamab. Patients who have achieved a MR or SD at completion of the 8 cycles may receive naxitamab + GM-CSF consolidation treatment for 5 cycles administered at every 8 weeks. The total number naxitamab cycles to be administered includes the treatment cycles administered in the HITS regimen

Missed dosing

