If a naxitamab dose is missed, administer the missed dose the following week, but the 3 infusions of naxitamab must be administered within a period of maximum 10 days. If a patient is treated on a modified schedule, the GM-CSF dosage will be the same as the standard on days -4 to 0, but GM-CSF will be administered at 500 μ g/m²/day on the day of the first infusion of naxitamab, on the day before and on the day of the second infusion of naxitamab, and on the day before and on the day of the third infusion of naxitamab. The modified schedule ensures that the same total dosage of GM-CSF is administered in the standard and in the modified schedules.

Laboratory assessments:

Laboratory tests should be performed as described in the table below and as clinically indicated.

Table 14 Protocol required laboratory assessments for patient treated with naxitamab + GM-CSF alone

Timing of Laboratory assessments	Parameters
All cycles*: Prior to dosing D-4, D1, D3, D5 EOT * If modified naxitamab dosing due to missed dose (ie naxitamab missed dose to be administered within the first 10 days of a cycle) check hematology parameters on day of last naxitamab administration in the cycle prior to administration of GM-CSF	Hematology 
 • Hemoglobin • Hematocrit • White blood cells (WBC) • Lymphocytes (absolute) • Neutrophils (absolute) • Eosinophils (absolute) • Basophils (absolute) • Monocytes (absolute) • Platelet count
All cycles: prior to dosing D1, D3, D5 EOT	Liver and kidney function blood tests 
 • ALT • AST • Alkaline phosphatase • Total bilirubin • LDH • BUN • Creatinine • Albumin (only prior to each cycle)
All cycles: prior to dosing D1, D3, D5 EOT	Serum electrolytes 
 • Sodium • Potassium
Prior to each cycle	Urine analysis (dipstick) 
 • Protein • Glucose • Leucocytes
Prior to each cycle EOT	Pregnancy test, if applicable Serum pregnancy test for WOCBP see 9.2.8 for further information
ADA Prior dosing in each cycle EOT	
 • Anti-naxitamab antibodies • Naxitamab AB (neutralizing effect)

The complete blood count (CBC) and differential counts should be repeated on sequential days during all treatment cycles if ANC is $> 20 \times 10^9/L$ or WBC $> 50 \times 10^9/L$ on the previous day.

Vital signs

- Prior to pre-medication (e.g., hydromorphone or morphine)
- Prior to start of naxitamab infusion

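### Appendix 2 schedules gabapentin only through Day 7 and does not re-time it when a missed naxitamab infusion is made up later, on the likeliest reading Days 8-10

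*Combined protocol and SAP*

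**What the plan says.** Section 8.4.1 warns: "Infusion with naxitamab is associated with pain that may be severe". It prescribes gabapentin at home to lower that risk, and refers patients who have stopped irinotecan/temozolomide (IT) for toxicity to Appendix 2 for the timing.

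Appendix 2, Pre-medication, gives one fixed window: "Gabapentin should be administered from Day -4 to Day 7 of each cycle according to local SoC". Dosing steps up over the first days and ends with "Day -2 and onwards until Day 7: 3 times daily". No taper is printed. Tables 12 and 13 mark premedication through Days 6+7. Naxitamab is given at 3 mg/kg on Days 1, 3 and 5.

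For a missed infusion, Appendix 2, Missed dosing, says: "administer the missed dose the following week, but the 3 infusions of naxitamab must be administered within a period of maximum 10 days". The Table 14 footnote states the limit in cycle days: "naxitamab missed dose to be administered within the first 10 days of a cycle".

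Two other items follow the infusions actually given. The higher GM-CSF dose is re-timed, ending "on the day before and on the day of the third infusion of naxitamab". The Table 14 footnote tells sites to "check hematology parameters on day of last naxitamab administration in the cycle prior to administration of GM-CSF". Neither place mentions gabapentin.

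**The concern.** The gabapentin window is fixed to cycle days, while the make-up infusion can move beyond it. A site that follows the printed days would then give a 3 mg/kg infusion with no gabapentin scheduled, although the protocol prescribes it for every standard infusion. Because GM-CSF and hematology are re-timed in the same part of the appendix, the silence on gabapentin looks like an oversight. Gabapentin is taken at home and built up over several days, so a family needs to know beforehand to keep going.

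The stakes are patient comfort and, to a small degree, the pain data. Pain during naxitamab infusions is secondary endpoint 14 (Section 6.2), is scored at all infusions (Section 9.2.7) and is summarised descriptively (Section 12.6).

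**Working it through.** **Inputs, all from Appendix 2.** Last scheduled gabapentin day: 7. Standard infusion days: 1, 3, 5. Make-up in the following week. Three infusions within at most 10 days (running text), or make-up within the first 10 days of the cycle (Table 14 footnote).

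**Check of the appendix's own claim.** It states that total GM-CSF is the same on both schedules.
- Standard: 5 × 250 + 5 × 500 = 3,750 µg/m².
- Modified: 5 × 250 + (1 + 2 + 2) × 500 = 3,750 µg/m².

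The claim reproduces, so the GM-CSF re-timing was worked out deliberately.

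**Make-up days.** Count the 10 days inclusively from the first infusion given, and take the following week to start on cycle Day 8. Limit = first infusion day + 9. Gap = make-up day − 7.

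| Missed dose | First infusion given | Limit, running text | Limit, Table 14 footnote | Make-up days meeting both | Gap |
|---|---|---|---|---|---|
| Day 3 or 5 | Day 1 | 1 + 9 = Day 10 | Day 10 | 8-10 | 1-3 days |
| Day 1 | Day 3 | 3 + 9 = Day 12 | Day 10 | 8-10 | 1-3 days |

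With Day 1 missed, the running text alone would allow Days 8-12 (gap 1-5 days). The footnote caps this at Day 10. Counting 10 elapsed days instead would give 1 + 10 = Day 11 or 3 + 10 = Day 13, but the footnote's Day 10 fits the inclusive count.

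**Other readings of the following week.**
- Same weekday, one week later: 1 + 7 = Day 8 and 3 + 7 = Day 10, both after Day 7. For a missed Day 5, 5 + 7 = Day 12 is past the Day 10 limit.
- Next calendar week, starting on Monday: if Day 1 is a Monday, the new week starts on Day 8, as in the table. If Day 1 is a Tuesday or Wednesday, it starts on Day 7 or Day 6, so a make-up on those days is covered. With a start on Day 6 and a limit of Day 10, 3 of the 5 possible days (8, 9, 10) are still uncovered.

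**Scheduled cover.** Before the standard Day 1 infusion a patient has had Days −4 to 0 = 5 days of gabapentin, of which Days −2 to 0 = 3 days at three times daily. Scheduled doses on an infusion day: 3 on each of Days 1, 3 and 5; 0 on Days 8-10.

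**With gabapentin tied to the infusions.** The standard schedule runs from the last infusion on Day 5 to the last gabapentin on Day 7, a 2-day tail at full frequency. Applied to a make-up infusion:
- Day 8: ends Day 10, 10 − 7 = 3 extra days.
- Day 9: ends Day 11, 4 extra days.
- Day 10: ends Day 12, 5 extra days.

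**The case against.** The best counter-argument is that the protocol leaves this to clinical judgement. Gabapentin follows local standard of care. Section 8.4.1 allows it to continue twice daily for up to a week if nerve pain lingers, and allows alternatives such as ketamine when pain control is inadequate. Section 8.4.7 allows any supportive treatment the patient needs. Opioids, antipyretic and the other hospital premedication go with each infusion rather than a cycle day, and Section 8.4.2 requires opioid rescue at the bedside. All of this stands. A reader might infer that gabapentin is forbidden after Day 7 or that the make-up infusion is given without analgesia; the documents support neither. But these clauses permit later gabapentin without scheduling it, and the lingering-pain clause concerns the period after naxitamab treatment, not prophylaxis before another infusion.

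The main regimen does not re-time gabapentin either. A missed dose there is given on Day 12 (Section 8.1.3), when gabapentin has been tapered to once daily (Section 8.4.1). So the protocol does not treat three-times-daily cover on a make-up day as essential. That is fair, and it limits the weight of the point. Still, the printed window in that regimen reaches the make-up day, and in Appendix 2 it may not.

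Table 13 might be read as showing that premedication is withheld on Days 8-10. It does not show that: its columns go from Days 6+7 to Days 11-28, so Days 8-10 are missing for every row, including naxitamab and GM-CSF.

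**Conclusion.** The point holds as a minor gap in scheduling. Gabapentin is printed through Day 7, nothing re-times it after a missed dose, and a make-up infusion on Days 8-10 comes 1-3 days after the last scheduled dose.

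This rests on reading the following week as cycle Day 8 onward, which the documents do not define. It cannot be said that every make-up infusion is uncovered, because under a calendar-week reading some are not. A 5-day gap should not be claimed either: Day 12 follows from the running text only, and the Table 14 footnote stops at Day 10.

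The group is narrow: patients who stopped IT for toxicity, continued naxitamab, missed an infusion and received it after Day 7. The documents give no frequency for this and no figure for how much pain gabapentin prevents. Pain scores at make-up infusions would be collected under different prophylaxis from the rest. A reader might infer a wider effect on efficacy, but nothing here touches the primary endpoint. Lowest severity.

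**What to change.** Add one sentence to Appendix 2 under Pre-medication, and repeat it under Missed dosing: on a modified schedule, gabapentin continues three times daily until 2 days after the last naxitamab infusion actually given. This matches the standard interval from the Day 5 infusion to the Day 7 end, which is at full frequency and not a taper. Add a note to Table 13 that premedication follows the last infusion given.

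The cost is 3-5 extra days of gabapentin, a drug already in use, in a cycle with a make-up on Days 8-10, and no new procedure. It would also help to define the following week in cycle days and to bring the 10-day rule in the text into line with the Table 14 footnote.

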11 LABORATORIES

11.1 Clinical Laboratory Assessments

The laboratory samples specified in [Table 9](#) will be measured by a local laboratory. Laboratory tests should be performed as described in [Table 9](#) and as clinically indicated. Please refer [Appendix 2](#) if the patient has discontinued IT treatment due to toxicity.

Table 9 Protocol required laboratory assessments

Timing of Laboratory assessments	Parameters

Screening
 
Cycle 1*: Prior to dosing D1, D5, and D8. In addition on D15
 
Subsequent cycles*: Prior to dosing D1, D5 and D8
 
EOT
 
*D10 all cycles: If modified naxitamab dosing due to missed dose (ie naxitamab to be administered on Day 12 and GM-CSF continued until Day 12)
	
Hematology
 
 • Hemoglobin • Hematocrit • White blood cells (WBC) Lymphocytes (absolute and %) • Neutrophils (absolute and %) • Eosinophils (absolute and %) • Basophils (absolute and %) • Monocytes (absolute and %) • Platelet count

Screening
 
Cycle 1: prior to dosing D1, D3, D5, D8 and D15
 
Subsequent cycles: prior to each cycle and D8
 
EOT
	
Liver and kidney function blood tests
 
 • ALT • AST • Alkaline phosphatase • Total bilirubin • Lactate dehydrogenase (LDH) • Blood urea nitrogen (BUN) • Creatinine • eGFR • Albumin (only prior to each cycle)

Screening
 
Cycle 1: prior to dosing D1, D3, D5, and D8
 
Subsequent cycles: prior to each cycle
 
EOT
	
Serum electrolytes
 
 • Sodium • Potassium • PO⁴ • Mg⁺⁺
Prior to each cycle	
Urine analysis (dipstick)
 
 • Protein • Glucose • Leucocytes

Screening
 
Prior to each cycle
 
EOT
	
Pregnancy test, if applicable
 
 • Serum pregnancy test for WOCBP see 9.2.8 for further information

The WBC and differential counts should be repeated on sequential days during all treatment cycles if ANC is $> 20 \times 10^9/L$ or WBC $> 50 \times 10^9/L$ on the day prior to GM-CSF treatment.

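### Appendix 2 promises an unchanged GM-CSF total after a missed naxitamab infusion, but the listed dosing days give more when a miss of the second or third infusion is known only on the day

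*Combined protocol and SAP*

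**What the plan says.** Appendix 2 of the protocol covers patients who stop irinotecan and temozolomide for toxicity and continue on naxitamab + GM-CSF in 28-day cycles. GM-CSF is given at 250 µg/m² on Days -4 to 0 and at 500 µg/m² "per day at Day 1 to Day 5". Naxitamab is given "on Days 1, 3, and 5 for a total dose of 9 mg/kg per cycle". The order within a day is also set: "On days when co-administered with GM-CSF, naxitamab infusion is started" at least 60 minutes after the GM-CSF dose.

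Under Missed dosing, a missed infusion moves to the following week, and all three infusions must fall within 10 days. The doses on Days -4 to 0 do not change. The 500 µg/m² doses then follow the infusions: one on the day of the first infusion, two "on the day before and on the day of the second infusion of naxitamab", and two placed the same way around the third. The paragraph closes with the assurance, which carries no condition: "The modified schedule ensures that the same total dosage of GM-CSF is administered in the standard and in the modified schedules".

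Table 14 schedules hematology before dosing on D-4, D1, D3 and D5. For a modified schedule it adds: "check hematology parameters on day of last naxitamab administration in the cycle prior to administration of GM-CSF".

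**The concern.** The rule starts when a dose is missed, and a miss is often not foreseen. By then the patient may already have taken 500 µg/m² doses that belonged to the infusion that did not take place. The rule lists further doses around the make-up infusion and is silent on those already taken. A site that follows the listed days would then exceed the total that the same paragraph guarantees.

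The situation is realistic on the protocol's own terms:

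- Same-day GM-CSF precedes the infusion by at least an hour.
- Section 8.4.5.3 gives a same-day reason not to start an infusion: blood pressure persistently at or above the 99th percentile must be treated first.
- Days 2 and 4 carry GM-CSF but no infusion. Section 8.1.2.4 foresees home administration, and Appendix 2 asks for a diary.
- Section 10.4 makes adverse events that lead to incomplete naxitamab dosing in a cycle an event of special interest.

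At stake is a clear dosing instruction in a mainly pediatric trial. Section 8.2 defines an overdose as more than 10% above the protocol-specified dose. It does not say whether that applies to cycle totals, and here the specified total is itself unclear.

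**Working it through.** **Inputs (Appendix 2).** GM-CSF 250 µg/m² on Days -4 to 0 (5 doses); 500 µg/m² on Days 1–5 (5 doses); naxitamab on Days 1, 3 and 5; make-up in the following week with all three infusions within 10 days, so on Days 8–10 if the first infusion was on Day 1.

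**The plan's own claim.** Standard cycle: 5 × 250 + 5 × 500 = 1,250 + 2,500 = 3,750 µg/m². This total is derived, not printed. For infusion days d1 < d2 < d3, the modified rule places 500 µg/m² on d1, d2−1, d2, d3−1 and d3, that is 1 + 2 + 2 = 5 doses. With the first infusion on Day 1, all 21 schedules that fit within 10 days with infusions at least two days apart give exactly 5. The claim therefore reproduces when the schedule is known in advance. For example:

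- Day 3 miss known before the Day 2 dose, make-up on Day 8: Days 1, 4, 5, 7, 8 = 5 doses.
- Day 5 miss known before the Day 4 dose, make-up on Day 8: Days 1, 2, 3, 7, 8 = 5 doses.

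**Miss known only on the day.** Count the 500 µg/m² doses already taken under Days 1–5, then add the rule days that remain. Make-up on Day 8 is shown; later permitted days give the same counts.

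| Infusion missed | That day's GM-CSF | Days with 500 µg/m² | Doses | Cycle total (µg/m²) |
|---|---|---|---|---|
| First (Day 1) | not taken | 3, 4, 5, 7, 8 | 5 | 3,750 |
| First (Day 1) | taken | 1, 3, 4, 5, 7, 8 | 6 | 4,250 |
| Second (Day 3) | not taken | 1, 2, 4, 5, 7, 8 | 6 | 4,250 |
| Second (Day 3) | taken | 1, 2, 3, 4, 5, 7, 8 | 7 | 4,750 |
| Third (Day 5) | not taken | 1, 2, 3, 4, 7, 8 | 6 | 4,250 |
| Third (Day 5) | taken | 1, 2, 3, 4, 5, 7, 8 | 7 | 4,750 |

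Totals: 1,250 + 6 × 500 = 4,250, and 4,250 / 3,750 = 1.133 (+13.3%); 1,250 + 7 × 500 = 4,750, and 4,750 / 3,750 = 1.267 (+26.7%).

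**Timing of the added blood count.** With the third infusion made up on Day 8, 9 or 10, GM-CSF resumes on Day 7, 8 or 9. The count that Table 14 adds falls on Day 8, 9 or 10, one day after resumption. The last scheduled count before resumption is D5, which is 7 − 5 = 2 to 9 − 5 = 4 days earlier.

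**The case against.** The strongest reply is that the printed rule contains no arithmetic error. It lists the 500 µg/m² days for a whole modified cycle, these add to five, and the assurance is true of the schedule described. The excess appears only if doses already taken are not deducted, and the text nowhere says to ignore them. This stands as far as it goes: the fault lies in the unspecified transition, not in the sum. It does not remove the conflict. If the assurance is a cap, some listed doses must be dropped and the text does not say which. If the listed days govern, the assurance fails.

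It is also fair that Section 8.1.3 lengthens GM-CSF from Days 6–10 to Days 6–12 after a miss in the four-drug regimen, so added GM-CSF days are not in themselves contrary to the protocol. But that section does not claim an unchanged total.

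The reach is small: only patients who have stopped irinotecan and temozolomide and then have an unforeseen miss. After an infusion reaction, Section 8.4.5 often leads to a slowed or paused infusion, and Section 7.12 stops all treatment after the listed severe reactions. Appendix 2 does not say whether a partly given infusion counts as missed.

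A reader might go further and infer that blood counts are checked only after GM-CSF resumes, so that the hold limits in Section 8.4.6 cannot be applied to the first resumed dose. The documents do not support this. The added check supplements the D-4, D1, D3 and D5 counts. Tests are also done when clinically indicated, and counts are repeated daily when the previous day's value exceeded the limits. Nor does Table 9 show an error by scheduling its extra count differently ("D10 all cycles: If modified naxitamab dosing due to missed dose"). It serves another regimen, and the difference is a matter of preference on timing.

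**Conclusion.** The concern holds in a limited form and is minor. The unconditional assurance is met when a miss is foreseen. It is not met, on a literal reading, when a miss of the second or third infusion becomes known only on the day: 6 or 7 doses of 500 µg/m² instead of 5. For a missed first infusion it fails only if that day's GM-CSF was already taken (6 doses). It would be wrong to infer that every missed infusion raises the total.

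These counts assume that one infusion is missed entirely, that doses already taken are not deducted, and that GM-CSF stops between the miss and the next listed day. The documents do not give the frequency of such misses, and no effect on the primary analysis is shown.

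A side note: the first resumed dose rests on the D5 count unless further tests are indicated or repeated. It is also unclear whether the D5 count, scheduled before dosing, is taken when nothing is dosed that day.

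**What to change.** Reconcile the two statements under Missed dosing in Appendix 2, in one of two ways:

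- State how GM-CSF doses already taken around a missed infusion are counted.
- Limit or delete the assurance, and print the totals that the rule gives for a miss of the first, second or third infusion.

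Which doses are to be given is the sponsor's clinical decision, and none is proposed here. The sponsor should also confirm that the timing of the added count in Table 14 is intended, and whether the D5 count is taken when there is no dosing on D5. The cost is a few lines of text in Appendix 2; the analysis does not change.
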